1.1 Synopsis	Sample size, intervention, duration in study for Panel D added	To expand the range of potential safe and efficacious doses
1.2 Scheme	Panel D added	To expand the range of potential safe and efficacious doses
1.3 SOA	Panel D added. Adjusted PK sample timepoints for Panel D, Period 2 (FRI period).	To expand the range of potential safe and efficacious doses
2	Changed to 4 panels	To expand the range of potential safe and efficacious doses
2.2.2 Pre-Clinical and Clinical Studies	Moved summary of PN003 to completed clinical studies section. Removed AE and PK table for PN 001	AE and PK tables for PN 001 are available in edition 3 of the IB.
2.2.3 Ongoing Clinical Studies	Updated safety and PK data of PN002 to date. Added summary for PN004	New data available

Section # and Name	Description of Change	Brief Rationale
3.0 Hypotheses, Objectives and Endpoints	Panel D added	To expand the range of potential safe and efficacious doses
4.1 Overall Design	Description of Panel D added to study design.	To expand the range of potential safe and efficacious doses
4.2 Scientific Rationale for Study Design	Rationale to explore 120 µg and 480 µg doses added	To expand the range of potential safe and efficacious doses
4.3,2 Maximum Dose/Exposure for this Study	Rationale for the highest dose 480 µg and estimated exposure of this dose added	To expand the range of potential safe and efficacious doses
5.1 Inclusion Criteria	Panel D added	To expand the range of potential safe and efficacious doses
5.2 Exclusion Criteria	Updated a- fib exclusion criteria. Removed Hep B exclusion criteria	To enhance recruitment for Panel D
6.1 Study Interventions Administered	Study interventions of 120µg and 480 µg for Panel D added. Device language removed	To expand the range of potential safe and efficacious doses. Device language is not applicable as it applies to marketed drug/device combination products.
6.3.1 Intervention Assignment	Sample allocation schedule for Panel D added	To expand the range of potential safe and efficacious doses
8.4.8 Device Events, Adverse Device Events	Device language removed	Device language is not applicable as it applies to marketed drug/device combination products

Section # and Name	Description of Change	Brief Rationale
8.7.1 Right Heart Catheterization Procedures	Language added if RHC procedure needs to stop earlier	RHC procedure may need to stop earlier at the discretion of the investigator.

1 PROTOCOL SUMMARY

1.1 Synopsis

Protocol Title: A Study to Assess the Effect of Single Doses of MK -5475 on Pulmonary Vascular Resistance in Patients with Moderate to Severe Pulmonary Arterial Hypertension

Short Title: Dosing of MK-5475 in Participants with Pulmonary Hypertension

Acronym: N/A

Hypotheses, Objectives, and Endpoints:

Hypotheses are aligned with objectives in the Objectives and Endpoints table.

This study is to be conducted in male and female participants with group 1 pulmonary arterial hypertension (PAH).

Primary Objectives	Primary Endpoints
- To evaluate the safety and tolerability of MK-5475 in participants with pulmonary arterial hypertension (PAH). (All parts)	Safety and tolerability will be evaluated during clinical assessments that include vital signs, safety laboratory testing, physical examinations, ECG readings, PFTs and review of adverse events.
- To assess the duration and effect following a single inhaled dose of MK-5475 on pulmonary vascular resistance (PVR) in participants with pulmonary arterial hypertension (PAH). (Part 2, Period 2 (Panel A) and Period 3 (Panels B, C and D))	Peak reduction from baseline in PVR after a single inhaled dose of MK-5475
Secondary Objectives	Secondary Endpoints
- To estimate the effect of MK-5475 given as single inhaled doses on systemic hemodynamic parameters (heart rate (HR), systolic and diastolic blood pressure (BP)) in participants with pulmonary arterial hypertension. (Part 2 Period 2 (Panel A) and Period 3 (Panels B, C and D))	- HR and BP change from baseline at 0.5, 4.5, and 24 (or prior to discharge) hours post-dose.
- To assess the effect following a single inhaled dose of MK-5475 on pulmonary blood volume (PBV) in participants with pulmonary arterial hypertension. (Part 2, Period 3 (Panel A) and Period 2 (Panels B, C and D))	- Increases from baseline PBV at 1, 3, 8 and 24 hours postdose.

Overall Design:

Study Phase	Phase 1
Primary Purpose	Treatment
Indication	Pulmonary Arterial Hypertension (PAH)
Population	Participants with moderate to severe Group 1 PAH
Study Type	Interventional
Intervention Model	Sequential This is a single-site study.
Type of Control	Not applicable
Study Blinding	Double-blind
Masking	Data Analyst
Estimated Duration of Study	The Sponsor estimates that the study will require approximately 22 months from the time the first participant signs the informed consent until the last participant's last study-related telephone call or visit.

Intervention Groups and Duration:

Intervention Groups	Intervention Group Name	Drug	Dose Strength	Dose Frequency	Route of Administration	Regimen/ Treatment Period/ Vaccination Regimen	Use
	Part 1 (Panel A)	MK-5475		120, 165, 240 µg	Single dose	Inhalation	Once/Periods 1-3
Pbo			0µg	Single dose	Inhalation	Once/ Periods 1-3	Pbo contro
Placebo			0µg	Single dose	Inhalation	Once/ Screening 2	Training
Part 2 (Panel A)	MK-5475		240 µg	Single dose	Inhalation	Once/Periods 2-3	Experimental
Part 2 (Panel B)	MK-5475		300, 360 µg	Single dose	Inhalation	Once/Periods 1-3 ^a	Experimental
	Pbo		0 µg	Single dose	Inhalation	Once/Screening 2	Training
Part 2 (Panel C)	Pbo		0 µg	Single dose	Inhalation	Once/Screening 2	Training
	MK-5475		300, 360 µg	Single dose	Inhalation	Once/Periods 1-3 ^{a,b}	Experimental
Part 2 (Panel D)	Pbo		0 µg	Single dose	Inhalation	Once/ Screening 2	Training
Part 2 (Panel D)	MK-5475		480, 120 µg	Single dose	Inhalation	Once/Periods 1 - 3	Experimental
Abbreviations: µg=micrograms; pbo=placebo							
^a Panel B and C: The dose of Part 2, Periods 2 and 3 (360 µg) will depend on the observance of adequate safety and tolerability in Part 2, Period 1							
^b Panel C dose will not exceed the maximum dose administered in Panel B.							
Total Number	4						
Duration of Participation	Each participant will participate in the study for approximately 15- 25 weeks for Panel A, 13 – 19 weeks for Panels B – C and 10 to 12 weeks for Panel D from the time the participant signs the Informed Consent Form through the final contact. After a screening phase of 5 weeks, each participant in Part 1 will receive 3 single doses of MK-5475/placebo over approximately 5 to 7 weeks. Participants in Part 2 will receive up to 2-3 single doses over approximately 3 to 8 weeks. Participants in Part 1 may participate in Part 2. After the end of treatment, each participant will be followed for 14 days.						

Number of Participants:

Approximately 8 participants in Part 1 and 24 participants in Part 2 will be allocated/randomized such that 8 evaluable participants in Part 1 and 24 evaluable participants in Part 2 complete the study as described in Section 9.5. Participants from Part 1 can participate in Part 2.

Study Governance Committees:

Steering Committee	No
Executive Oversight Committee	No
Data Monitoring Committee	No
Clinical Adjudication Committee	No
Insert Other Oversight Committee	No
Study governance considerations are outlined in Appendix 1.	

Study Accepts Healthy Volunteers: No

A list of abbreviations used in this document can be found in Appendix 13.

1.2 Schema

The study design is depicted in [Table 1](#). Detailed depiction of Part 2, Periods 2 and 3 are in [Figure 1](#) and [Figure 2](#).

Table 1 Overall Study Design

Panel	Part 1 Period 1	Part 1 Period 2	PK Break	Part 1 Period 3	Part 2 Period 1 ^c	Part 2 Period 2 ^c	Part 2 Period 3
A (N=8) ^b	120µg/ Pbo ^a	165µg/ Pbo ^a		240µg/ Pbo ^a		240 µg w/ Right Heart Catheterization (RHC) ^{a, d}	240 w/ Functional Respiratory Imaging (FRI) ^{a, d}
B (N=4) ^d					300 µg ^{a, d}	360 µg w/ Functional Respiratory Imaging (FRI) ^a	360 µg w/ Right Heart Catheterization (RHC) ^a
C (N= up to 8) ^b					300 µg ^a	360 µg w/ Functional Respiratory Imaging (FRI) ^a	360 µg w/ Right Heart Catheterization (RHC) ^a
D (N= up to 7) ^b					480 µg ^c	120 µg w/ Functional Respiratory Imaging (FRI) ^a	120 µg w/ Right Heart Catheterization (RHC) ^a

a. The suggested doses may be adjusted downward based on evaluation of safety, tolerability, pharmacokinetic and/or pharmacodynamic data observed in previous intervention periods. Refer to Section 6.6 (Dose Modification) for the safety, pharmacokinetic, and pharmacodynamic data that will be reviewed prior to dose escalation.
 
b. Participants in Part 1 may continue to participate in Part 2 provided they meet RHC criteria at baseline Part 2 Period 2. The minimum sample size for Panel C = 6 but, may increase based on the number of participants from Panel A who do not move forward to Part 2 or fail to meet the baseline RHC criteria in Period 2. The maximum sample size for Panel D = 7 but, will depend upon the total number of participants enrolled in Panel C at the time Panel D begins. Total sample size in Part 2 equals 24.
 
c. Participants in Panel A that continue into Part 2 will not have a Period 1 but, will go directly to Period 2 where RHC is performed. This period can occur in parallel with Panel B, Period 1. Panel C, Period 1 may begin following review of PK from Panel B Period 1 (Parallel with Periods 2 or 3 of Panel B).
 
d. A rolling evaluation of PK may occur for participants in Panel B and C, Period 1. Review of Panel B PK for Period 1 will occur before dosing of Panel B, Period 2 and Panel C, Period 1. Panel C, Period 2 may begin following review of PK for the first 4 participants of Panel C.
 
e. Panel D, may occur in parallel with participants already actively enrolled in Panel C.
							

Period 2 Day 1 RHC/Dosing/ Safety and Other Procedures	Wash out	Period 3 Day 1 FRI/Dosing/Safety and Other Procedures	Post Study
Pre RHC > Predose RHC > Dosing > Post dose RHC > D/C	≥ 7 days	Pre scan > Predose FRI > Dosing > Post dose FRI > D/C	~ 14 Days

Figure 1 Part 2 Panel A Study Design (Periods 2 and 3)

Period 2 Day 1 FRI/Dosing/ Safety and Other Procedures	Wash out	Period 3 Day 1 RHC/Dosing/Safety and Other Procedures	Post Study
Pre scan > Predose FRI > Dosing > Post dose FRI > D/C	≥ 7 days	Pre RHC > Predose RHC > Dosing > Post dose RHC > D/C	~ 14 Days

Figure 2 Part 2 Panel B, C and D Study Design (Periods 2 and 3)

1.3 Schedule of Activities (SoA)

Study Period	Screening			Intervention (Panel A: Part 1, Periods 1-3) (Panel B, C and D: Part 2, Period 1)												Notes
	≤ 35 days pre-randomization	≤ 7 days pre-randomization	Day 1	Hours												
Scheduled Hour, Day	Screening 1	Screening 2	Pre-dose	0	~0.1 (5min)	0.25 (15min)	0.5 (30min)	1	2	3	4	8	24	Post Study ~14 days		
Administrative Procedures																
Informed Consent	X															
Informed Consent for Future Biomedical Research	X															
Inclusion/Exclusion Criteria	X	X	X												Pre-dose assessment applies to Period 1 only	
Participant Identification Card	X															
Medical History	X															
Prior/Concomitant Medication Review	X	X	X	X	X	X	X	X	X	X	X	X	X	X	X	
Assignment of Screening Number	X															
Assignment of Allocation Number (Randomization)			X												Period 1 only. All participants receive an allocation number.	
MK-5475/pbo Administration				X											Placebo applies to Part 1 – Panel A	
Standard Meals												X	X		See section 5.3.1 for timing of meals and snacks	

Study Period	Screening			Intervention (Panel A: Part 1, Periods 1-3) (Panel B, C and D: Part 2, Period 1)												Notes	
	≤ 35 days pre-randomization	≤ 7 days pre-randomization	Day 1	Hours													
Scheduled Hour, Day	Screening 1	Screening 2	Pre-dose	0	~0.1 (5min)	0.25 (15min)	0.5 (30min)	1	2	3	4	8	24	Post Study ~14 days			
Domiciling			X	-----X													See Section 8.1.11 for domiciling details
Training with Spirometer Device (PFTs)		X														Training will be done for each participant at one occasion for site spirometry measures.	
Inhaler Training/Placebo Administration		X														Preferably done at Screening 2 but, may be done at Screening 1 if within 7 days of pre-randomization.	
Inspiratory Flow Meter Assessment		X	X													Panels B, C and D only. Day 1 procedure can be done within 3 hours at predose.	
Safety Procedures																	
Full physical examination (PE)	X		X											X	X	Pre-dose measure is	
Height	X															prior to each	

Study Period	Screening			Intervention (Panel A: Part 1, Periods 1-3) (Panel B, C and D: Part 2, Period 1)											Notes
	≤ 35 days pre-randomization	≤ 7 days pre-randomization	Day 1	Hours											
Scheduled Hour, Day	Screening 1	Screening 2	Pre-dose	0	~0.1 (5min)	0.25 (15min)	0.5 (30min)	1	2	3	4	8	24	Post Study ~14 days	
Weight	X													X	period. See section 8.3.1 for PE, height and weight procedures and 8.11.5 for timing window.
Heart Rate(HR) & Blood Pressure(BP)	X		X				X	X	X		X	X	X	X	Pre-dose measure is prior to each period. See section 8.3.2 for all appropriate vital sign procedures and 8.11.5 for timing window.
Orthostatic Vital Signs (HR & BP)	X		X								X		X	X	
Body Temperature(Temp)	X		X								X		X	X	
Respiratory Rate (RR)	X		X				X	X	X		X	X	X	X	
12-lead ECG	X		X				X	X	X		X	X	X	X	Pre-dose measure is prior to each period. See section 8.3.3 for ECG procedure details and 8.11.5 for timing window.

Study Period	Screening			Intervention (Panel A: Part 1, Periods 1-3) (Panel B, C and D: Part 2, Period 1)												Notes
	≤ 35 days pre-randomization	≤ 7 days pre-randomization	Day 1	Hours												
Scheduled Hour, Day	Screening 1	Screening 2	Pre-dose	0	~0.1 (5min)	0.25 (15min)	0.5 (30min)	1	2	3	4	8	24	Post Study ~14 days		
Pulmonary Function Tests (PFTs)	X		X						X				X	X	Pre-dose measure is prior to each period. See section 8.3.5 for specific parameters to be performed at screening and pre / post-dose and 8.11.5 for timing window.	
Serum β-Human Chorionic Gonadotropin (β-hCG; WOCBP only)	X													X		
Urine Pregnancy Test (WOCBP only)			X												Pre-dose measure is prior to each period	
Serum Follicle Stimulating Hormone (FSH) - (WONCBP only)	X															
Echocardiogram (if needed, for Panel B or C participants only)	X														Follow site SOP for assessment of PAH in newly diagnosed participants in Panel B, C or D only	
HIV, hepatitis B and C screen (per site SOP)	X															

Study Period	Screening			Intervention (Panel A: Part 1, Periods 1-3) (Panel B, C and D: Part 2, Period 1)												Notes
	≤ 35 days pre-randomization	≤ 7 days pre-randomization	Day 1	Hours												
Scheduled Hour, Day	Screening 1	Screening 2	Pre-dose	0	~0.1 (5min)	0.25 (15min)	0.5 (30min)	1	2	3	4	8	24	Post Study ~14 days		
Urine/Blood Drug Screen (UDS/BDS) (per site SOP)	X		X												Screening and Period 1 UDB/BDS is mandatory, any additional UDS/BDS are conducted per site SOP	
Hematology/Chemistry	X		X										X	X	See Appendix 2 for laboratory tests	
Urinalysis	X		X										X	X		
PT/aPTT	X		X										X	X		
AE/SAE review	X	X	X-----X											X	See all sections under 8.4	
Phone Call for AE/SAE review														X	Panel A participants that go into Part 2 will have a phone call only 14 days after last dosing period.	
Pharmacokinetics																
Blood for Plasma MK-5475 parent and/or metabolites			X		X	X	X	X	X	X	X	X	X		Pre-dose measure is prior to each period. See operations manual for sample processing details.	

Study Period	Screening			Intervention (Panel A: Part 1, Periods 1-3) (Panel B, C and D: Part 2, Period 1)												Notes
	≤ 35 days pre-randomization	≤ 7 days pre-randomization	Day 1	Hours												
Scheduled Hour, Day	Screening 1	Screening 2	Pre-dose	0	~0.1 (5min)	0.25 (15min)	0.5 (30min)	1	2	3	4	8	24	Post Study ~14 days	All post study procedures to be performed for participants in Panel A. that do not go onto Part 2.	
Biomarkers																
Blood for Genetic Analysis			X												Pre-dose Period 1 only – See Section 8.8 and 8.9	

Part 2											
Study Period	Intervention (FRI Period) Panel A = Period 3 Panel B, C and D = Period 2									Notes	
	Day 1		Hour								
Scheduled Time	Predose and Pre Baseline Scan	Baseline Scan	0	1	3	8	Prior to Discharge post 8 hr scan (if needed)	24	Prior to Discharge post 24 hr scan	Post Study	Post Study procedures are performed following the completion of Period 3 (All Panels)
Administrative Procedures											
Prior/Concomitant Medication Review	X	X	X	X	X			X		X	
MK-5475 Administration			X								
Inspiratory Flow Meter Assessment	X									X	Assessment to be done within 3 hours at predose (Panels B, C and D only). Post Study assessment (Panel A only) An optional predose assessment may be done for Panel A.
Standard Meals				X-----X							A standard snack may be given between the 1 and 3 hour CT scans. Meal will be given about 1 hour after 3 hour postdose scan. See 5.3.1
Safety Procedures											
Full physical examination (PE)	X									X	Pre-dose PE may occur w/in 24 hrs of baseline scan
Weight	X										
Heart Rate(HR) & Blood Pressure(BP)	X						X		X	X	See section 8.3.2 for all appropriate vital sign procedures.
Body Temperature(Temp)	X						X		X	X	
Respiratory Rate (RR)	X						X		X	X	
12-lead ECG	X						X		X	X	
Serum β -Human Chorionic Gonadotropin (β -hCG; WOCBP only)										X	

Part 2												
Study Period	Intervention (FRI Period) Panel A = Period 3 Panel B, C and D = Period 2									Notes		
	Day 1		Hour									
Scheduled Time	Predose and Pre Baseline Scan	Baseline Scan	0	1	3	8	Prior to Discharge post 8 hr scan (if needed)	24	Prior to Discharge post 24 hr scan	Post Study	Post Study procedures are performed following the completion of Period 3 (All Panels)	
Urine Pregnancy Test (WOCBP only)	X										See Appendix 10.2 for details regarding laboratory tests. Pre-dose lab tests may occur w/in 24 hrs of baseline scan	
Hematology/Chemistry	X									X		
Urinalysis	X									X		
PT/aPTT	X									X		
PFTs										X		
AE/SAE review	X	X	X	X	X	X	X	X	X	X	See all sections under 8.4	
Pharmacokinetics												
Blood for Plasma MK-5475 and or Metabolites Assay	X		X-----X									Panels A, B and C: Predose, 1, 3, 8 and 24 hours postdose. Panel D: Predose, 15 min, 30 min, 1, 2, 3, 4, 8 and 24 hours postdose See operations manual for sample processing details
Pharmacodynamics												
CT Scan for Functional Respiratory Imaging (FRI)		X		X	X	X			X		Baseline scan to occur w/in 30 minutes of dosing	

Part 2													
Study Period	Intervention (RHC Period)											Notes	
	Panel A = Period 2 Panel B, C and D = Period 3												
	Day 1	Day 1	Hour										
Scheduled Hour, Day	Pre RHC	Pre dose	0	0.25	0.5	1	2	3	4	4.5	24h or prior to D/C		
Administrative Procedures													
RHC Inclusion/Exclusion Criteria		X										Pre-dose assessment applies to Period 2 if Panel A and Period 3, if Panel B, C or D	
Prior/Concomitant Medication Review	X-----X												
MK-5475 Administration			X										
Inspiratory Flow Meter Assessment		X										Assessment to be done within 3 hours at predose (Panels B, C and D). An optional predose assessment may be done for Panel A.	
Standard Meals							X				X	See section 5.3.1 for timing of meals and snacks	
Domiciling	X-----X												
Pharmacodynamic Procedures													
Right Heart Catheterization (RHC) Measurements		X			X	X	X	X	X	X		See section 8.7.1 and operations manual for RHC details	
Pulmonary Arterial Pressure (PAP)		X	X-----X									q 30 minutes	
Arterial O ₂ Saturation (pulse oximetry)		X			X	X	X	X	X	X		On room air	
Mixed Venous O ₂ Saturation (MVO ₂)		X			X	X	X	X	X	X		On room air	
Safety Procedures													
Full physical examination	X										X	Pre RHC PE may occur w/in 24 hours of dosing	
Heart Rate (HR) & Blood Pressure (BP)	X	X			X-----X						X	HR/BP q 30 minutes	
Body Temperature (Temp)	X										X	See section 8.3.2 for all appropriate vital sign procedures.	
Respiratory Rate (RR)	X				X	X	X	X	X	X	X		
12-lead ECG	X										X	X	See section 8.3.3 for ECG procedure details

Part 2													
Study Period	Intervention (RHC Period) Panel A = Period 2 Panel B, C and D = Period 3											Notes	
	Day 1	Day 1	Hour										
Scheduled Hour, Day	Pre RHC	Pre dose	0	0.25	0.5	1	2	3	4	4.5	24h or prior to D/C		
Urine Pregnancy Test (WOCBP only)	X												
Hematology/Chemistry	X										X	See Appendix 10.2 for details regarding laboratory tests. Pre RHC labs may occur w/in 24 hrs	
Urinalysis	X										X		
PT/aPTT	X										X		
AE/SAE review	X	X	X -----X									X	See all sections under 8.4
Pharmacokinetics													
Blood for Plasma MK-5475 and or Metabolites Assay		X		X	X	X	X	X	X	X		See operations manual for sample processing details	

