6.6.1 Stopping Rules

The following stopping rules will be employed during the conduct of this study.

If any of the below stopping rules are met, the study will be paused and no further dosing will occur until the Sponsor has reviewed the totality of data available. In order to continue the study (upon joint agreement with the Sponsor and investigator), a substantial amendment will be submitted for approval.

1. An individual participant reports a Serious Adverse Event considered related to the study drug by the investigator.
2. Two (2) or more participants within a Panel (at the same dose level) report Severe Non-serious Adverse Events considered related to the study drug by the investigator.

If any of the below stopping rules are met, subsequent higher doses will be lowered based upon joint agreement of the Sponsor and investigator in order for the study to continue.

Panel wide stopping criteria

- a. Should the emerging PK (mean) data indicate that the maximum clinical exposure (C_{max} or AUC), as defined in Section 4.3 will be exceeded, subsequent higher doses will be adjusted based upon joint agreement of the Sponsor and investigator.

1. Individual stopping criteria:

- a. Hemodynamic changes that exceed the pre-specified limitations (See Appendix 10)

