8.3 Safety Assessments

Details regarding specific safety procedures/assessments to be performed in this study are provided. The total amount of blood/tissue to be drawn/collected over the course of the study (from prestudy to poststudy visits), including approximate blood/tissue volumes drawn/collected by visit and by sample type per participant, can be found in Appendix 8.

Planned time points for all safety assessments are provided in the SoA.

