10.10 Appendix 10: Hemodynamic Stopping Criteria

Hemodynamic stopping criteria

Individual stopping criteria

During any of the treatment periods, if a particular participant demonstrates a **sustained change** (defined below) in any *one* of the following parameters, that participant will not participate in additional dose escalation. For assessing change from baseline, post-dose values will be compared to the Day 1 predose baseline established by 3 semi-recumbent measurements of heart rate and blood pressure obtained ~1-2 minutes apart within 3 hours prior to dosing.

Participants meeting individual hemodynamic stopping criteria may be re-challenged in this study only after consultation or discussion between the primary investigator and the sponsor.

During any of the treatment periods if a particular participant demonstrates change in any *one* of the following parameters lasting ≥ 90 minutes, dose escalation in that participant will be halted and the participant may be withdrawn from the study or re-challenged at the same dose or at a lower dose. Participants that meet criteria listed below will be followed up until parameters no longer meet stopping rule criteria. Each participant will individually define his limit for continuation. Stopping rules will apply for a particular participant when he demonstrates a **sustained change** (at least 4 triplicate measurements or at least 1 triplicate measurement every 30 min of which the median result of each triplicate measurement will account for checking the stopping criteria) of ≥ 90 minutes in any *one* of the following criteria during the postdose period:

Heart rate:

- 1) Resting HR increase over the predose baseline of ≥ 25 bpm.
- 2) Resting HR > 120 bpm

Blood pressure:

- 1) Resting SBP reduction > 25 mmHg over the predose baseline.
- 2) Resting SBP < 90 mmHg or participant placed in the Trendelenburg position.
- 3) Resting SBP ≥ 180 mmHg
- 4) Resting DBP < 50 mmHg or DBP ≥ 110 mmHg

Blood pressure and heart rate:

- 1) For any participants: > 20 mmHg drop in resting SBP and > 20 bpm rise in resting HR
- 2) For any participants: > 30 mmHg drop in orthostatic SBP and > 30 bpm rise in orthostatic HR

Definitions for HR and BP

Participants must be resting and semirecumbent for *at least* 10 minutes prior to obtaining *any* measurements used to limit dose escalation (except for changes noted while obtaining orthostatic signs).

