Baseline HR and BP: Predose baseline values will be determined for each specific period. For the investigator, the baseline will be calculated using the median from the triplicate measurements obtained approximately 1-2 minutes apart within approximately 3 hours prior to dosing to determine that change from baseline. For all formal statistical testing, the mean baseline will be used to calculate the change from baseline.

Sustained changes are defined as lasting greater than or equal to 90 minutes. If any of the resting, semi-recumbent or orthostatic parameters defined above are exceeded, that participant must remain resting and semi-recumbent for at least the next 90 minutes. During that time, BP (systolic and diastolic) and HR will be obtained every 30 minutes (i.e., at 30, 60, and 90 minutes following). If a participant's BP (systolic *or* diastolic), *or* heart rate exceeds the parameters for the median of *all three* of the following three 30-minute periods, this is defined as a sustained finding, and dosing will end for that particular participant. Following 90 minutes, if, in the opinion of the investigator, the participant requires further observation, the participant will remain resting and semi-recumbent until HR and/or BP return to baseline. For HR and BP that are out of range, if the recheck is within normal range this is not considered a sustained change.

Notes

If an assessment of the present and previous periods raises safety and tolerability concerns though individual participant/participants do *not* meet the criteria described above, and after discussion with the investigator and the Merck monitor, dose escalation for the entire panel may end.

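### At the first 360 µg dose in Panels B and C (Part 2 Period 2, FRI), no HR/BP is scheduled between dosing and the check after the 8 h scan, so neither Appendix 10 nor the review before Period 3 has a near-peak reading

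*Combined protocol and SAP*

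**What the plan says.** - **Source of time points.** Section 8.3: "Planned time points for all safety assessments are provided in the SoA".
- **Dose order.** Table 1 (Section 1.2) gives Panels B and C 300 µg in Part 2 Period 1, then "360 µg w/ Functional Respiratory Imaging (FRI)" in Period 2, then 360 µg again with RHC in Period 3.
- **FRI schedule (Section 1.3).** HR/BP is marked at predose, under "Prior to Discharge post 8 hr scan (if needed)", before discharge after the 24 h scan, and post study. The 0, 1, 3 and 8 h columns are blank. Temperature and respiratory rate follow the same pattern. Under Section 8.1.11, same-day discharge comes about an hour after the 8 h scan ends, and an overnight stay is at the investigator's discretion.
- **Other periods.** Part 2 Period 1 has HR/BP at 0.5, 1, 2, 4, 8 and 24 h. The RHC period has "HR/BP q 30 minutes".
- **Stopping rule.** The only individual criterion in Section 6.6.1 is "Hemodynamic changes that exceed the pre-specified limitations (See Appendix 10)". Appendix 10 applies it in any treatment period. Once a limit is exceeded, "During that time, BP (systolic and diastolic) and HR will be obtained every 30 minutes". If all three rechecks exceed it, "this is defined as a sustained finding, and dosing will end for that particular participant". The same appendix says that participants who meet the criteria "may be re-challenged in this study only after consultation or discussion between the primary investigator and the sponsor", and it allows the same or a lower dose.
- **Review.** Section 8.11.2 has the investigator and the sponsor review vital signs from the previous period, up to 24 h, before Periods 2 and 3.

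**The concern.** The Appendix 10 rechecks at 30, 60 and 90 minutes begin only when a reading is out of range. In the FRI period the schedule supplies no such reading until most of the drug is expected to have cleared. An asymptomatic change that resolved before about 8 h would leave no trace in the scheduled data. The review before Period 3 would then rest, for vital signs, on readings taken well after the peak. The gap falls in the period where Panels B and C move from 300 to 360 µg, and the periods on either side are monitored far more closely. At stake are the decision on a second 360 µg dose for that participant and the completeness of the 360 µg vital-sign record, which belongs to the primary safety endpoint.

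**Working it through.** **1. Scheduled post-dose HR/BP times, up to 8 h after dosing**

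| Period (Panels B, C) | Dose | Times | Count |
|---|---|---|---|
| Period 1 | 300 µg | 0.5, 1, 2, 4, 8 h | 5 |
| Period 2, FRI | 360 µg (first) | none before the discharge check | 0 |
| Period 3, RHC | 360 µg | every 30 min, 0.5 to 4.5 h | (4.5 − 0.5)/0.5 + 1 = 9 |

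A one-column misalignment in the FRI table would still leave 1 h and 3 h blank. Sections 8.3.2.1 and 8.11.5 give the triplicate method and the time windows. They add no FRI time points.

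**2. Where the first reading falls relative to peak**

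Inputs: median Tmax 1 h and half-life about 2 h (Sections 2.2.2 and 4.3.3). The Tmax is from healthy participants at 15 to 165 µg. That both values hold in PAH at 360 µg is an assumption.

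Model: one compartment, first-order absorption, C(t) ∝ exp(−ke·t) − exp(−ka·t). Here ke = ln 2 / 2 = 0.347/h, and ka is set so that ln(ka/ke)/(ka − ke) = 1 h, giving ka = 2.19/h.

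At the peak: exp(−0.347) − exp(−2.19) = 0.707 − 0.112 = 0.595.

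- 8 h: 0.0625 / 0.595 = 0.105 of Cmax
- 9 h: 0.0442 / 0.595 = 0.074 of Cmax

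Concentration is at or above half of Cmax only from about 0.2 to 3.5 h. With half-life 1.5, 2 or 3 h crossed with Tmax 0.5, 1 or 2 h, the 8 h value ranges from 0.034 to 0.332 and the 9 h value from 0.022 to 0.264. This locates readings relative to exposure. It is not a model of haemodynamic effect.

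**3. What a scheduled reading could still catch**

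The first reading at 8 to 9 h plus 90 minutes of rechecks ends at 9.5 to 10.5 h. From a scheduled reading, the rule can be met only by a change still present at 8 to 9 h that persists to that time.

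**4. Candidate added times**

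| Time | Base case, share of Cmax | Range over the grid |
|---|---|---|
| 0.5 h | 0.85 | 0.53 to 1.00 |
| 2 h | 0.82 | 0.55 to 1.00 |
| 4 h | 0.42 | 0.22 to 0.79 |

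**5. Fit with the CT scans (minutes after dosing)**

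Scan window ±20 minutes (Section 8.11.5); time in scanner up to 15 + 15 = 30 minutes (Section 8.7.2).

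- 1 h scan: 60 − 20 = 40 to 60 + 20 + 30 = 110
- 3 h scan: 180 − 20 = 160 to 180 + 20 + 30 = 230
- Readings (10 minutes of rest, then 2 to 4 minutes for triplicates): 20–34, 110–124 and 230–244

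The first readings do not overlap the scans, before allowing for scan preparation. The rechecks can overlap:

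- Exceedance at 30: rechecks at 60, 90 and 120. The first two fall within 40–110.
- Exceedance at 120: rechecks at 150, 180 and 210. The last two fall within 160–230.
- Exceedance at 240: rechecks at 270, 300 and 330. No scan falls there.

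Appendix 10 requires semi-recumbent rest for those 90 minutes and the scans are supine, so the plan needs to say which comes first.

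**6. Who is still affected**

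Not stated. Section 2.2.3 reports on 18 participants, which equals 8 + 4 + 6 if Panels A and B are full. Section 4.3.3 says doses up to 360 µg have been given in Panels B and C. Assume Panel B is complete and at least one Panel C participant has had 360 µg. Then 0 to 6 − 1 = 5 remain if Panel C stays at 6, or 0 to 8 − 1 = 7 if it reaches the 8 in Table 1. Panel C at 8 with Panel D at 7 would give 8 + 4 + 8 + 7 = 27, above the limit of 25 in Section 4.1, so Panel D would then have to be smaller.

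**The case against.** Several points on the other side stand.

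- **The rule does not bar Period 3 dosing outright.** A reader might infer that a detected change would have stopped the second 360 µg dose. The documents do not support that. Section 6.6.1 lowers subsequent higher doses, and Panels B and C have none after FRI. Appendix 10 ends dosing on a sustained finding in one paragraph but allows same-dose re-challenge after consultation in others. A scheduled reading would prompt that consultation; it would not fix its outcome.
- **The rule is not disabled.** A reader might also infer that only a symptom could trigger it. Section 8 allows further evaluation whenever the investigator or sponsor thinks it necessary for safety, and AE review is scheduled through the FRI day. The operations and imaging manuals are not available and may add monitoring. The gap is in scheduled readings.
- **The escalation itself is supported.** The move to 360 µg depends on Period 1, which has a full HR/BP schedule. The step is 360/300 = 1.2-fold, and the highest individual AUC0-24 reported at 360 µg (6.99 nM·hr) is below the highest at 300 µg (7.25 nM·hr).
- **Near-peak HR/BP at 360 µg is collected in Period 3**, every 30 minutes, and Section 4.3.2 reports no effect on heart rate or blood pressure in any clinical study so far.
- **The affected group may be empty.**

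These points limit the consequence. None of them supplies a scheduled near-peak reading at the first 360 µg dose, and an asymptomatic transient change would still depend on someone choosing to look.

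**Conclusion.** The gap is real and minor. At the first 360 µg dose in Panels B and C there are 0 scheduled HR/BP readings before the discharge check, against 5 up to 8 h at 300 µg and 9 up to 4.5 h at the repeat 360 µg dose. The first scheduled reading is expected at about 11% to 7% of peak concentration (2% to 33% across the assumptions), or near 24 h if an overnight stay means the earlier check is not needed. The Appendix 10 rule and the Section 8.11.2 review therefore lack a scheduled near-peak reading for this dose. The table reading is firm. The practical effect is less certain, because the manuals are unseen and the number still to be dosed is not stated. The point does not extend to Panel A, which had 240 µg under the full Part 1 schedule or the RHC schedule before FRI, or to Panel D, whose FRI dose is 120 µg after 480 µg in Period 1.

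**What to change.** The sponsor should first confirm whether any Panel B or C participant still awaits a first 360 µg dose. If none does, no schedule change is needed. Otherwise choose one of the following.

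**Option 1: amend the FRI schedule.** Add triplicate HR/BP at about 0.5, 2 and 4 h. State that if a limit is exceeded, the 30, 60 and 90 minute rechecks take precedence over the 1 h or 3 h CT scan, which may be delayed or omitted. This is consistent with Section 8.11.5, which ranks urgent safety checks above routine procedures. Take the 4 h reading before the meal. Cost: 3 × 12 to 14 = 36 to 42 minutes per participant, in people already on site, plus a short amendment, because Section 8.11.6 allows changes in safety timing but not more procedures per participant. A participant who triggers the rule may have one PBV time point delayed or lost.

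**Option 2: run RHC before FRI for these participants.** Section 8.11.6 already permits this, documented by a letter to the study file, and Panel A uses this order. It gives HR/BP every 30 minutes at the first 360 µg dose with no added procedure. Cost: a participant who fails the baseline RHC criteria is discontinued (Section 7.1) and would contribute no FRI data.
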